4. **Research Plan:** Summarize the study design and research procedures using non-technical language that can be readily understood by someone outside the discipline. **Be sure to distinguish between standard of care vs. research procedures when applicable, and include any flowcharts of visits specifying their individual times and lengths.** Describe the setting in which the research will take place.

Study Sites/Feasibility. The study will be conducted in at clinical office for Aware Recovery Center (North Haven, CT). The census of the facility on average recruits 38 new individuals a month and they currently have 300. This will be the first study, completed at this site, which is a randomized control treatment design.

Procedure:

(www.randomized.com). Individuals will be placed into one of two conditions (Soberlink+Aware; Named Group 1) or (Aware; Named Group 2). Both groups will be consented by either the principal investigator or the research assistants who will be present at all screenings and ensured that they understand their rights. Participants will be told they are allowed to leave or withdraw for the study without penalty or hindering the relationship between themselves and Aware Recovery.

Figure 2: Time Intervals for Assessments

Group 1

This group will include access to the Aware treatment (see 'Aware treatment' below), and access to the Soberlink device. A research assistant will train the participant and provide an orientation (see orientation to Soberlink below) for what will be taught. All participants will be complete screening and outcome assessments, along with using the Soberlink device for the first time. The participant's Soberlink device will be set up to test participants twice a day. Reminder emails (see attached reminder emails) will be sent out the day before, and the day of the 1 month, 2 month and 3-month surveys that will be completed online in the participant's home through a secure link sent directly to them. Subsequent phone calls will be made by the research assistant to the participant if they have missed their evaluation. Upon completion of the surveys, the participants in group 1 will be paid, and reminded of the subsequent follow-ups. The estimated time of the process will take 45 to 60 minutes to complete.

Orientation to Soberlink

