Individuals who miss two consecutive BAC's will be followed up by either Research Assistant or the PI. Individuals who miss four consecutive BAC's without contact of the PI or the research assistant will be temporarily hold unless the individual has expressed thoughts of leaving the study prematurely. Missing more than six consecutive BACs without communication will result in termination from the study by the PI. A pilot study contacted at Aware prior to the PI being involved demonstrated little reactivity or premature departure for those who had access to the Soberlink device.

Aware/Group 2:

This group will not receive access or training to Soberlink device, however they will be recruited to complete the same set of surveys at the same time intervals (See Figure 2). Upon completion of the surveys, the participants in group 2 will be paid, and told reminded the subsequent follow-ups. Reminder emails (see attached reminder emails) will be sent out the day before, and the day of the 1 month, 2 month and 3 month evaluations. Subsequent phone calls will be made by the research assistant to the participant if they have missed their evaluation. The estimated time of the process will take under 30 minutes to complete.

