We are planning to assess a broad range of subject characteristics, process measures and treatment outcomes over the 3-month trial and at the 6 week post treatment follow-up (See Table 1). Baseline assessments are designed to ensure that patients meet eligibility criteria and that important predictor variables such as cognitive impairment are assessed. Baseline measures include evaluation and understanding of the extent of the AUD issue from a several different vantages points. Primary outcome measures include reductions in days per week of use and negative BAU screens for alcohol. Monthly assessments will take approximately 30 minutes and monthly and follow-up's 45 minutes. Patients will be paid \$10 for the baseline and monthly assessments, \$25 for follow-up assessments (up to \$65 total).

active alcohol use disorders.

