13. **Statistical Considerations:** Describe the statistical analyses that support the study design. A sample size of 110 would provide >80% power (α = .05) to detect a medium to large effect size (d= .65) and allow to fully evaluate gender differences. Greater power is provided by the repeated measures GEE and LMM analysis for the primary outcomes of BAC screen negative for alcohol drugs and days/month of self-reported illicit drug use. Sample size calculations for LMM are dependent on the number of repeated events, the retention rate, and the interclass correlation, in addition to the alpha level, the expected effect size, and the statistical power 198. The current randomized trial would provide estimates to guide a power analysis for a large Stage II study. Statistical procedures and models for analyzing data have been selected according to the research hypotheses being investigated and the types of data available. We will use α < .05, but will use appropriate corrections for multiple tests. Statistical analyses will be conducted on an intention-to-treat sample using SPSS. Using chi square and t-tests, we will first conduct preliminary analyses of the adequacy of the randomization procedure, the comparability of baseline measures for the two groups, and the possible need for covariates in the analyses of treatment outcome data.

SECTION II: RESEARCH INVOLVING DRUGS, BIOLOGICS, RADIOTRACERS, PLACEBOS AND DEVICES

ft
his
section
(or one
of its part
s. A or B
() is not
applicable.
check o
ff N/A
and de
lete the
rest of th
e section.

A.	RADIOTRACERS ⊠N/A	
1.	Name of the radiotracer: Write here	
2.	Is the radiotracer FDA approved? □YES	□NO

- If NO, an FDA issued IND is required for the investigational use unless RDRC assumes oversight.
- 4. **Background Information:** Provide a description of previous human use, known risks, and data addressing dosage(s), interval(s), route(s) of administration, and any other factors that might influence risks. If this is the first time this radiotracer is being administered to humans, include relevant data on animal models.

Check one: □IND# Write here or □RDRC oversight (RDRC approval will be required prior to use)

Write here

3.

4. **Source:** Identify the source of the radiotracer to be used. *Write here*

5. **Storage, Preparation and Use:** Describe the method of storage, preparation, stability information, method of sterilization and method of testing sterility and pyrogenicity.

Write here

R	DRUGS/BIOLOGICS

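### Covariates for the self-reported days outcome are left to baseline balance tests and none is named; fixing baseline days of alcohol use in advance is a cheap, modest gain in precision.

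*Combined protocol and SAP*

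**What the plan says.** Section I.13 (Statistical Considerations) holds the only statement on covariates. Chi-square and t-tests come first, to check whether randomization worked and to look at "the comparability of baseline measures for the two groups, and the possible need for covariates in the analyses of treatment outcome data". No cut-off is given and no covariate is named for any outcome. The primary outcomes are to be analysed by repeated-measures GEE and LMM, but the plan does not say how the baseline value enters: as a covariate, as a first repeated response, or not at all.

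Section I.4 (Assessments) says the baseline battery ensures that "important predictor variables such as cognitive impairment are assessed". None of these predictors is carried into an outcome model.

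The self-reported outcome is worded in two ways. Section I.4 has "Primary outcome measures include reductions in days per week of use and negative BAU screens for alcohol". Section I.13 has "BAC screen negative for alcohol drugs and days/month of self-reported illicit drug use".

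On purpose, Section I.13 adds: "The current randomized trial would provide estimates to guide a power analysis for a large Stage II study".

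**The concern.** In a randomized trial, a baseline difference with p < .05 is a chance event. It occurs in about 5% of trials for any baseline variable, whether or not that variable predicts outcome. Adjustment earns its precision from the correlation between baseline and outcome, and the balance test does not measure that. If a .05 cut-off is applied, a useful predictor is left out of the model in about 95% of trials; at .20, in about 80%.

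Two things are at stake. The first is precision: the trial is meant to supply estimates for planning a Stage II study, so the width of the interval matters as well as significance. The second is discretion: covariates would be chosen with data in hand, by a rule the plan does not state.

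The point covers only the self-reported days outcome. Of Group 2 the protocol says "This group will not receive access or training to Soberlink device", so that arm has no device breath screens and no between-arm contrast to adjust.

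**Working it through.** **Inputs from the plan.** N = 110, alpha .05, d = .65, power above 80% (Section I.13). Equal allocation, so 55 per arm (Section I.4, Randomization). Follow-ups at months 1, 2 and 3.

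**Assumptions.** Two-sided test, because sidedness is not stated. Rho from 0 to .5, because none is given; it may be low, since participants are already in treatment at entry (Section I.8). A .05 balance-test cut-off, because none is given. Normal data, one follow-up and full retention unless noted.

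**1. The plan's own figure.** SE of the difference in SD units = sqrt(2/55) = .1907. Then .65/.1907 = 3.41. Power is 92.6% by the normal approximation and 92.2% by the noncentral t. The claim of more than 80% holds without any covariate.

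**2. Interval width.** Unadjusted 95% half-width = 1.982 × .1907 = .378, times the mean of the sample SD (about 1 − 1/(4 × 108) = .998) = .377 SD. With one fixed covariate, variance is multiplied by (1 − rho²) × (1 + 1/(N − 4)). The second term is the price of estimating the slope: 1 + 1/106 = 1.0094, or 1.0047 on the SE.

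| rho | sqrt(1 − rho²) × 1.0047 | half-width (SD) |
|---|---|---|
| .1 | 1.000 | .377 |
| .2 | .984 | .371 |
| .3 | .958 | .361 |
| .5 | .870 | .328 |

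Break-even is at rho² = .0094/1.0094, so rho is about .1.

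**3. Power (%), simulation, 40,000 trials per row, 55 per arm.** Test-then-adjust means the baseline covariate enters only if its balance test has p < .05.

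| d | rho | never adjust | test-then-adjust | fixed adjustment | fixed minus test-then-adjust |
|---|---|---|---|---|---|
| .65 | 0 | 92.2 | 92.1 | 92.0 | −0.1 |
| .65 | .1 | 92.1 | 92.1 | 92.1 | 0.0 |
| .65 | .2 | 91.8 | 91.9 | 92.6 | 0.7 |
| .65 | .3 | 92.1 | 92.4 | 94.0 | 1.6 |
| .65 | .5 | 92.1 | 92.9 | 97.2 | 4.3 |
| .50 | 0 | 73.7 | 73.6 | 73.3 | −0.3 |
| .50 | .2 | 73.9 | 74.0 | 75.2 | 1.2 |
| .50 | .3 | 73.8 | 74.0 | 77.2 | 3.2 |
| .50 | .5 | 73.8 | 74.8 | 84.8 | 10.0 |

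Test-then-adjust barely improves on never adjusting. Across runs, the cost of fixed adjustment at rho 0 is about 0.2 to 0.5 points.

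**4. False positives under test-then-adjust at .05.** 4.8% (rho .3), 4.5% (.5) and 3.5% (.7): slightly conservative, not inflated.

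**5. Sensitivity at d = .65, test-then-adjust v fixed.** With an assumed 20% loss (44 per arm): 85.3 v 86.1 (rho .2), 85.8 v 88.2 (.3), 86.7 v 93.7 (.5). With skewed days bounded at 0 to 30 and observed rho of .23, .36 and .55: 92.8 v 93.6, 93.1 v 95.1, 93.3 v 97.7. With the mean of three months (correlation .5 among months): 98.5 v 98.8, 98.8 v 99.3, 98.9 v 99.9 at rho .2, .3, .5.

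**6. Baseline as a repeated response.** An LMM with a common baseline mean across arms comes within 0.6 points of fixed adjustment in every setting tried. Its null rejection rate was .051 to .060 with a simple Wald test, so it needs small-sample degrees of freedom.

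**The case against.** The strongest reply is that little is at stake. The plan's power claim is met without adjustment, the text speaks only of a possible need and sets no cut-off, and rho is unknown. If most participants are already abstinent at entry, rho could be near .1 and the gain vanishes. If the analyst fits an LMM with a common baseline mean, nearly all the gain is already there. All of this stands, and it is why the point is only an optional improvement. It does not rescue balance tests as the criterion, since they are uninformative about predictive value at any cut-off.

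A reader might infer a much larger loss from the wording of the outcome as a reduction in use. A change-score LMM with a separate baseline mean in each arm would, at d = .65 and rho .2, reach 76% against 93% with one follow-up, or 85% against 99% over three months: a gap of 14 to 17 points. The documents do not support that reading. A reduction describes the outcome, not a model, and no change-score analysis is specified. It is only a secondary reason to fix the model in advance.

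A reader might also infer that no baseline of the outcome is collected, because Table 1 lists the TLFB only under outcome measures. That does not follow. At the Group 1 orientation session "All participants will be complete screening and outcome assessments", and Group 2 is to "complete the same set of surveys at the same time intervals". The Randomization paragraph has alcohol use assessed at that visit, and Table 1 lists a baseline Substance Use History that records frequency. Figure 2, which shows the assessment times, could not be read here, so no gap can be claimed; it only needs confirming.

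**Conclusion.** The concern holds as a modest, low-cost improvement for the self-reported days outcome. Choosing covariates by balance test forgoes precision and leaves discretion open. It does not undermine the stated power and does not inflate false positives.

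The size depends on rho, which the documents do not give. At d = .65 with one follow-up the gain in power runs from nil (rho .1) to 4 to 5 points (rho .5); at d = .50, from about 1 point (rho .2) to about 10 (rho .5). At rho .5 the interval narrows by about 13% (.377 to .328 SD); at rho .2, by under 2% (.377 to .371 SD). The comparison with test-then-adjust also assumes a .05 cut-off that the plan does not state.

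**What to change.** 1. Reconcile the two descriptions of the outcome in Sections I.4 and I.13 as days of alcohol use over one stated window. This comes first, because the useful covariate is the baseline of the same variable.
2. Confirm in one line that this measure (for example the 30-day TLFB) is taken at baseline in both arms.
3. Keep the check on randomization and the descriptive baseline table. Change only the covariate clause, to:

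> The primary LMM of days of alcohol use adjusts for baseline days of alcohol use as a fixed covariate, whatever the baseline balance; baseline tests do not determine covariates for this outcome. Any other covariate for this outcome is named before outcome data are seen.

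An acceptable alternative, if fixed in advance, is an LMM with baseline as a repeated response and a common baseline mean across arms, run with small-sample degrees of freedom. It also keeps participants whose baseline value is missing.

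The planned gender analyses and the provisions for other outcomes are unaffected. Do not extend the change to the breath-screen outcome.

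The cost is wording, one confirmation, and one degree of freedom.
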